8.2.3.5. Exploratory Analyses

Not applicable.

8.2.4. Effectiveness Analyses

8.2.4.1. Death

Deaths will be summarized in terms of number and proportion of patients by cause of death (cardiovascular, non-cardiovascular, unknown) and detailed cause of death (cardiovascular: cardiac failure, myocardial infarction, arrhythmia, stroke or cerebrovascular accident, others; non-cardiovascular: neoplasm malignant, infection, others).

All-cause deaths and cardiovascular deaths will be analyzed in the following manner:

- "8.1.3. Binary Variables" will be followed for binary variables, and
- "8.1.4. Time-to-event Data" will be followed for time-to-event data.

In the Kaplan-Meier analysis, a patient whose date of death is unknown will be handled as follows:

➤ If the date of final confirmation of survival is on Week 52 or earlier and the information of death was obtained on Week 52 or earlier,

the patient is handled as interval censored data between the date of final confirmation of survival and the date of death information:

If the date of final confirmation of survival is on Week 52 or earlier and the information of death was obtained after Week 52.

the patient is handled as a patient who was alive on the date of final confirmation of survival;

➤ If the date of final confirmation of survival is after Week 52 and the information of death was obtained after Week 52,

the patient is handled as a patient who was alive at Week 52 (Day 364).

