8.1.4. Time-to-event Data

Mortality at one year from the start of treatment will be estimated using the Kaplan-Meier method. Kaplan-Meier plots (displaying the number of at-risk patients every one month) will also be presented.

Analyses Based on the Person-Year Method

The incidence of an event per observation time will, if it is presented, be calculated using the formula:

Incidence (events/100 person-year) = $100 \times y/PT$ y: Number of events PT: Total observation time (years),

where the observation time is determined in conformity with the part "Follow-up Status" in "8.2.2. Patient Characteristics and Medical History". In addition, its 95% CI will be presented according to the formula ¹:

$$\left[\frac{100}{PT} \times \frac{1}{2} \chi_{2y}^{2}(\alpha/2), \frac{100}{PT} \times \frac{1}{2} \chi_{2(y+1)}^{2}(1-\alpha/2)\right]$$

y: Number of events

 $\chi^2_{2y}(\alpha/2)$: The $\alpha/2$ percentage point of the chi-square distribution of 2y degrees of freedom

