For both Safety Analysis Set and Effectiveness Analysis Set, the following dosing data of Selara tablets will be summarized for the overall population and by eCLCr (<30 mL/min, 30 - <50 mL/min, ≥50 mL/min, unknown):

- Duration of treatment (continuous)
- Duration of treatment [for each of the periods defined in Appendix A1.1 (excluding the Final Visit)]
- Mean daily dose (continuous)
- Mean daily dose [for each of the periods defined in Appendix A1.1 (excluding the Final Visit)]

Reason for discontinuation [within 26 weeks: inadequate clinical response, AEs, others;
 after 26 weeks: inadequate clinical response, AEs, no revisit, others]

The duration of treatment is defined as the period from the first administration to the last administration in this study, including non-dosing periods. If the date of the last administration is unknown for a patient who discontinued treatment, the date on which the patient was first seen by the physician after the discontinuation will be considered as the date of the last administration.

• Follow-up Status

For the Effectiveness Analysis Set, the duration of follow-up (continuous) will be summarized. The duration of follow-up for a patient will be calculated as follows.

When the patient survived at Week 52,

Duration of follow-up = 52 weeks (364 days).

When the survival status of the patient is "unknown" at Week 52,

Duration of follow-up = date of final confirmation of survival – date of first administration in this study + 1 (days).

When the patient died by Week 52,

if the date of death is known,

Duration of follow-up = date of death - date of first administration in this study + 1 (days),

if the date of death is unknown.

Duration of follow-up = date of final confirmation of survival – date of first administration in this study + 1 (days).

• Estimated Creatinine Clearance (eCLCr) and Estimated Glomerular Filtration Rate (eGFR)

Scatter plots (x-axis: baseline eCLCr, y-axis: baseline eGFR) will be presented. The number of data and the Pearson product-moment correlation coefficient will be presented.

• Subgroup Analyses

For both Safety Analysis Set and Effectiveness Analysis Set, statistics will be presented according to Section 8.1 with respect to the following patient characteristics:

- Sex [male, female]
- Age [<15 years, 15 <65 years, 65 <75 years, ≥75 years]
- NYHA class [I, II, III, IV, not assessed/unknown]
- Diabetes mellitus with microalbuminuria or proteinuria [present, absent, unknown]

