8.2.4.4. Subgroup Analyses

According to the categorizations defined in Section 5.4, subgroup analyses will be performed regarding deaths and clinical effectiveness (as assessed by the physician).

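### Kaplan-Meier for cardiovascular death, with no competing-risk rule, biases one-year cardiovascular mortality slightly upward

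*SAP*

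**What the plan says.** SAP 8.2.4.1 treats the two death endpoints alike: "All-cause deaths and cardiovascular deaths will be analyzed in the following manner". The binary form follows SAP 8.1.3 (number and proportion, exact interval when one is shown). The time-to-event form follows SAP 8.1.4, where "Mortality at one year from the start of treatment will be estimated using the Kaplan-Meier method". SAP 8.1.4 also provides a rate per 100 person-years.

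The only special rules in 8.2.4.1 concern deaths with an unknown date. The SAP does not say how a non-cardiovascular death, or a death of unknown cause, enters the cardiovascular curve, and it names no cumulative incidence method. Both kinds of death are identified, however: "Deaths will be summarized in terms of number and proportion of patients by cause of death (cardiovascular, non-cardiovascular, unknown").

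Under Follow-up Status in SAP 8.2.2, a patient with a known date of death has "Duration of follow-up = date of death - date of first administration in this study + 1 (days"), whatever the cause. A patient whose survival status at Week 52 is unknown is followed to the last confirmation of survival.

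SAP 8.2.4.4 adds that "subgroup analyses will be performed regarding deaths and clinical effectiveness", using the categories of SAP 5.4, which include eCLCr, age and NYHA class. Protocol 7.2.6.2 and 7.7 plan to compare overall and cardiovascular mortality with the domestic Phase III study or Japanese epidemiological studies, and SAP 8.2.4.5.1 defines subpopulations for the mortality comparisons.

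**The concern.** A patient who dies of cancer or infection can no longer die of a cardiovascular cause. A Kaplan-Meier curve for cardiovascular death that drops this patient at death without an event treats the patient as still able to have one later. One minus that curve estimates cardiovascular mortality in a hypothetical setting without other deaths (and only if the causes are independent). It does not estimate the proportion who die of cardiovascular causes within a year. It lies above that proportion whenever other deaths precede some of the cardiovascular ones.

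The figure matters because it is to be set beside outside studies and may be repeated by subgroup. The excess grows with mortality, so it would not be the same in low-risk and high-risk groups.

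**Working it through.** **What can be reproduced.** The documents state no cardiovascular mortality, so there is no plan figure to reproduce on this point. The precision ranges in Protocol 7.5.2 do reproduce (for example 1.14% to 5.06% for a true rate of 3.1% in 300 patients, given there as 1.1% to 5.1%), but they do not bear on it.

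**Inputs.**
- One-year all-cause mortality A: 7.3% and 8.9% (Protocol 7.2.6.2).
- Planned size: 1000 patients (Protocol 7.5.1).
- Horizon: 364 days (SAP 8.2.2).
- Assumed, not in the documents: cardiovascular share of deaths s of 50% to 80%; subgroup mortality of 20%, 30% or 40%; subgroup size of 150.

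**Formulas**, with constant cause-specific hazards over the year:
- H = −ln(1 − A)
- Cumulative incidence of cardiovascular death: CIF = s × A
- Kaplan-Meier with other deaths censored: KM = 1 − exp(−s × H)

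Example with A = 8.9% and s = 60%: H = 0.0932, CIF = 0.60 × 8.9% = 5.34%, KM = 1 − exp(−0.0559) = 5.44%, excess 0.10 points.

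| A | s | CIF | KM | Excess (points) |
|---|---|---|---|---|
| 7.3% | 50% | 3.65% | 3.72% | 0.07 |
| 7.3% | 80% | 5.84% | 5.88% | 0.04 |
| 8.9% | 50% | 4.45% | 4.55% | 0.10 |
| 8.9% | 80% | 7.12% | 7.19% | 0.07 |
| 20% (assumed) | 50% | 10.00% | 10.56% | 0.56 |
| 20% (assumed) | 80% | 16.00% | 16.35% | 0.35 |
| 30% (assumed) | 50% | 15.00% | 16.33% | 1.33 |
| 30% (assumed) | 80% | 24.00% | 24.82% | 0.82 |
| 40% (assumed) | 50% | 20.00% | 22.54% | 2.54 |
| 40% (assumed) | 80% | 32.00% | 33.55% | 1.55 |

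**Worst timing.** If every non-cardiovascular death came before any cardiovascular death, KM = sA / (1 − (1 − s)A). At A = 8.9% and s = 50% this is 4.45% / (1 − 0.0445) = 4.66%, an excess of 0.21 points.

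**Sampling error.** The 95% half-width, 1.96 × √(CIF × (1 − CIF)/N), is 1.16 to 1.59 points for the whole cohort (N = 1000) over the range above. For an assumed subgroup of 150 at 30% mortality it is 5.7 to 6.8 points.

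**Effect on a subgroup contrast.** Take a group at 30% and a group at 8.9%, both with s = 50%. The difference is 16.33 − 4.55 = 11.78 points by Kaplan-Meier and 15.00 − 4.45 = 10.55 points by cumulative incidence, so the contrast is widened by about 1.2 points.

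**Whether the crude proportion is a substitute.** With complete Week 52 status it equals the CIF. With exponential loss, where d is the fraction lost by one year and L = −ln(1 − d), it is s × H/(H + L) × (1 − exp(−(H + L))). At A = 8.9% and s = 70% the CIF is 6.23%. The crude proportion is 5.92%, 5.59% and 5.25% for d = 10%, 20% and 30%, which is 0.31 to 0.98 points too low. Under the same inputs Kaplan-Meier is 6.32%, or 0.09 points too high.

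**The case against.** The strongest reply is that nothing important turns on this. At the documents' own mortality the excess is far below sampling error. Effectiveness is a secondary objective (Protocol 6.3), all tests are exploratory (SAP 4.1) and there is no decision rule (SAP 4.2). All of that stands, and it keeps the point minor.

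Second, Kaplan-Meier is not the only planned figure. The person-year rate is a valid cause-specific rate and does not have this bias. The crude proportion does not have it either, but it runs low when Week 52 status is unknown, so it is not a full replacement.

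Third, if an outside comparator used Kaplan-Meier for cardiovascular death, the same method gives the like-for-like comparison. The documents do not say what the comparators used. This supports showing the Kaplan-Meier figure beside such a comparator, not using it as the main estimate.

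Fourth, counting unknown-cause deaths as competing events could cost more than the correction gains. If 10% of deaths at 8.9% mortality were of unknown cause and half of those were cardiovascular (both assumed), cardiovascular mortality would be understated by 8.9% × 0.10 × 0.5 = 0.45 points. Kaplan-Meier would drop those deaths without an event too, so this does not favour it. It does call for a sensitivity analysis.

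Two stronger readings are tempting. A reader might infer that subgroup differences will be exaggerated. The documents do not establish this: SAP 8.2.4.4 does not say which death analyses are repeated by subgroup, no subgroup mortality is given, and SAP 5.4 allows small subgroups to be reviewed patient by patient. A reader might also infer that the reported cause-specific figures will add up to more than all-cause mortality. Two such Kaplan-Meier curves would do so (9.07% against 8.9% at s = 70%), but the SAP plans no curve for non-cardiovascular death, and its tabulated proportions by cause sum to all deaths.

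**Conclusion.** The mismatch between estimator and target is real and its direction is clear. That non-cardiovascular deaths are censored is an inference: the SAP does not say so, but it names Kaplan-Meier, ends follow-up at any death and gives no other rule.

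For the whole cohort the upward bias is about 0.04 to 0.10 points, given 7.3% to 8.9% all-cause mortality, an assumed cardiovascular share of 50% to 80% and constant hazards. It would be about 0.2 points at most under extreme timing. It would not change a conclusion about the cohort. If Kaplan-Meier is repeated by subgroup, which is the natural but not the only reading, the excess could be about 1 point at an assumed 30% mortality, and subgroup contrasts may be modestly exaggerated. That too would lie well within the sampling error of a subgroup of 150. All-cause Kaplan-Meier is unaffected.

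**What to change.** In SAP 8.2.4.1:
- Estimate one-year cardiovascular mortality with the cumulative incidence function (Aalen-Johansen), with non-cardiovascular death as a competing event.
- Treat deaths of unknown cause as competing events in the main analysis and as cardiovascular in a sensitivity analysis.
- Keep Kaplan-Meier for all-cause death. Show the cardiovascular Kaplan-Meier figure only beside a published comparator that used it, after checking which estimator each comparator used.
- State in 8.2.4.4 which death analyses are repeated by subgroup, and use the same estimator there.

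Cause of death, date of death and survival confirmation are already collected (Protocol 7.3.8 and 7.3.9), so no new data are needed. The cost is a few sentences in the SAP, a standard procedure option and slightly more analysis work. The unknown-date rules in 8.2.4.1 are worded for Kaplan-Meier and would have to be restated for the new estimator.

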8.2.4.2. NYHA Class

NYHA class data at baseline and final visit will be summarized in shift tables (I, II, III, IV, not assessed/unknown).

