7.3.6.1. NYHA Functional Classification

For clinical evaluation, enter whether or not evaluation based on NYHA Functional Classification is done and the evaluation result. The evaluation result to be entered should be the one obtained on the last day of the observation period. If treatment with this drug is discontinued, enter the result of evaluation implemented on the last day of observation. However, if no evaluation is done in the relevant period, enter the evaluation result obtained in the period closest to the relevant period.

- (1) Whether or not evaluation based on the NYHA Functional Classification is done
- (2) Date of evaluation based on the NYHA Functional Classification

(3) Results of evaluation based on the NYHA Functional Classification

Reference) NYHA Functional Classification

- Class I: Having a heart disease, but with no limitation of physical activity. Ordinary physical activity does not cause marked fatigue, palpitations, dyspnoea, or anginal pain.
- Class II: Having a mild limitation of physical activity. No symptom at rest. Ordinary physical activity causes fatigue, palpitations, dyspnoea, or anginal pain.
- Class III: Having a severe limitation of physical activity. No symptom at rest. Exertion less than ordinary activity causes fatigue, palpitations, dyspnoea, or anginal pain.
- Class IV: Any physical activity is limited due to a heart disease. A symptom of heart failure or anginal pain is present even at rest. These symptoms can be exacerbated by slight exertion.

(Source: Igaku Shoin's Medical Dictionary 2nd Edition, issued on February 15, 2009)

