8. STATISTICAL METHODS AND ANALYSES

Unless otherwise stated, for patients who completed treatment, data within the first 52 weeks (364 days) + 30 days (= 394 days) will be included in each statistical analysis. For patients who discontinued treatment, data until the first visit after discontinuation of treatment with Selara tablets, or the date 30 days after the last treatment, whichever comes first, will be included. For patients who died, all data will be included.

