11. APPENDICES

11.1. Appendix 1: Details of Data Extraction

A1.1 Definition of Visits for the Assessment of Dosing Status and Safety Endpoints

Visit	Endpoints	Representative date	Definition (time window)	
Baseline	Dosing status, safety endpoints	Day 1	From 30 days before the date of the first dose in this study (the date of the start of	
	outry trapellie		treatment) to the date of treatment start (before dosing)	
Week 1	Dosing status,	Day 7	From the date of treatment start (after	
	safety endpoints		dosing) to 17 days after treatment start	
Week 4	Dosing status, safety endpoints	Day 28	18-42 days after treatment start	
Week 8	Dosing status, safety endpoints	Day 56	43-70 days after treatment start	
Week 12	Dosing status, safety endpoints	Day 84	71-98 days after treatment start	
Week 16	Dosing status, safety endpoints	Day 112	99-126 days after treatment start	
Week 20	Dosing status, safety endpoints	Day 140	127-154 days after treatment start	
Week 36	Dosing status, safety endpoints	Day 252	155-266 days after treatment start	
Week 52	Dosing status, safety endpoints	Day 364	267-394 days after treatment start	
Final	Dosing status,		The time when the final visit for this study	
Visit	safety endpoints		is made	

If multiple sets of observation data are reported on different dates within a time window, data on the date closest to the representative one will be used for summarization/analysis. If two sets of data are reported on two dates equally close to the representative one, the data on the later date will be adopted. If there are multiple values observed on the same day, the mean value of them will be used.

A1.2 Definition of Visits for Cardiac Function Classification

Visit	Endpoints	Representative Date	Definition (time window)
Baseline	Left ventricular ejection fraction (LVEF), left ventricle internal dimensions in diastole (LVDd), left atrial dimension (LAD)	Day 1	From 180 days before the date of the first dose in this study (the date of the start of treatment) to the date of treatment start (before dosing)
Week 26	LVEF, LVDd, LAD	Day 182	From the date of the start of treatment (after dosing) to 182 days after treatment start
Week 52	LVEF, LVDd, LAD	Day 364	183-394 days after treatment start

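### The NYHA shift table has no category for death, so patients who died can appear at a class recorded before death or as not assessed/unknown

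*SAP*

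**What the plan says.** SAP 6.2 lists NYHA class as an effectiveness endpoint, and SAP 8.2.4.2 gives its whole analysis in one sentence: "NYHA class data at baseline and final visit will be summarized in shift tables (I, II, III, IV, not assessed/unknown".

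The value that feeds the final-visit side comes from Protocol 7.3.6.1. The target is the class on the last day of the observation period. Two rules cover departures from it:

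- After stopping treatment: "If treatment with this drug is discontinued, enter the result of evaluation implemented on the last day of observation".
- When nothing was assessed at the right time: "However, if no evaluation is done in the relevant period, enter the evaluation result obtained in the period closest to the relevant period".

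Neither rule mentions death. SAP 8 says only "For patients who died, all data will be included".

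Deaths have their own analysis in SAP 8.2.4.1: "Deaths will be summarized in terms of number and proportion of patients by cause of death (cardiovascular, non-cardiovascular, unknown". An exact confidence interval, a Kaplan-Meier estimate and a person-year rate are also planned. SAP 8.2.4.4 adds that "subgroup analyses will be performed regarding deaths and clinical effectiveness (as assessed by the physician", using the groups in SAP 5.4, which include NYHA class and treatment status.

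**The concern.** A baseline-by-final table invites the reader to judge how many patients moved up, stayed or moved down. A patient who died has no class at the end of the year. If the last class before death was the same as or better than at baseline, that patient stands in the same cell as a survivor who held or gained ground. The protocol itself describes the life prognosis of these patients as poor, so the number need not be trivial.

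At stake is a fair reading of one listed effectiveness endpoint under a secondary objective. The primary safety objective is not touched.

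**Working it through.** **Where a patient who died ends up**

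1. SAP 8.2.4.2 offers five final-visit categories, none of them death.
2. Protocol 7.3.6.1 calls for the closest available evaluation. For a patient who died, any such evaluation predates death.
3. SAP 8 retains all data for patients who died, so the value is kept.
4. SAP 7 sets out-of-window observations to missing by reference to Appendices A1.1 to A1.3, but NYHA is named in none of them. A1.1 covers dosing status and safety endpoints and describes Final Visit only as "The time when the final visit for this study" is made. A1.2 lists LVEF, LVDd and LAD. A1.3 lists BNP and NT-proBNP. No limit is therefore set on the age of the carried class.
5. With no evaluation to enter, the patient falls under not assessed/unknown. With no effectiveness assessment at all, the patient is outside the Effectiveness Analysis Set (SAP 5.2).

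**Size**

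The documents give no figure for NYHA shifts, so there is no planned number to reproduce. Inputs:

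- N = 1000, the planned safety analysis set (Protocol 7.5.1).
- m = one-year mortality. Protocol 7.2.6.2 quotes 7.3% and 8.9% from two outside cohorts; applying them here is an assumption.
- w = share of survivors whose class worsened. Assumed 10%, for illustration.
- d = share of those who died whose last recorded class had already worsened. Unknown, so run from 0 to 100%.

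Expected deaths are N × m: 1000 × 0.073 = 73 and 1000 × 0.089 = 89.

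If death is ranked below class IV, the share worsened is (1 − m)w + m:

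- m = 7.3%: 0.927 × 0.10 + 0.073 = 16.6%
- m = 8.9%: 0.911 × 0.10 + 0.089 = 18.0%

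If every patient who died is shown at the last recorded class, the planned table gives (1 − m)w + m·d. The gap is m(1 − d), which does not depend on w:

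| d | Table, m = 7.3% | Gap (points) | Table, m = 8.9% | Gap (points) |
|---|---|---|---|---|
| 0% | 9.3% | 7.3 | 9.1% | 8.9 |
| 50% | 12.9% | 3.7 | 13.6% | 4.5 |
| 100% | 16.6% | 0 | 18.0% | 0 |

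At an assumed mortality of 3% the gap is at most 3 points. Under this ranking it never runs the other way.

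The improved share behaves similarly. If 30% of survivors improved (assumption), placing deaths outside the improved group gives 0.927 × 0.30 = 27.8% or 0.911 × 0.30 = 27.3%. The planned table would show 30.0% if those who died carried an improved class equally often, and 27.8% or 27.3% if none did.

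If those who died are all under not assessed/unknown, the improved and unchanged shares of all patients are the same as with a 'died' column. They rise only if a reader drops the unknowns from the denominator (30.0% improved in the example), which the SAP does not say to do.

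**The case against.** Several points on the other side are sound.

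- **Deaths are reported, and by starting class.** SAP 8.2.4.4 applies the SAP 5.4 groups to deaths, and NYHA class is one of them. A reader might infer that the plan hides deaths; it does not. What remains is that deaths per baseline class do not show which final-class cells hold patients who died. NYHA shifts are not split by survival or treatment status either.
- **No improved or worsened proportion is planned.** SAP 8.2.4.2 specifies a table, with no summary share and no test. Any such share would be derived by the reader.
- **Death is not on the NYHA scale.** Protocol 7.3.6.1 defines classes I to IV. Ranking death below IV creates a composite, and SAP 8.2.4.1 separates deaths from malignancy or infection, which are not plainly functional decline. This argues for a separate column, and against counting deaths as worsened in the main display.
- **Some final classes are valid.** After discontinuation, observation ends at the first consultation (Protocol 7.2.6.1), while survival is followed to Week 52 (Protocol 7.3.9). A patient who stopped, was assessed and died later has a genuine final class, so not all of the 73 to 89 would be misplaced.
- **The mortality is borrowed.** One source cohort was restricted to systolic dysfunction, whereas this study enrols on treatment for CHF. The 1000 is also the safety set, which can be larger than the effectiveness set.

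These points limit the size and keep the matter minor. None of them takes patients who died out of the final-class cells.

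**Conclusion.** The point holds as a gap in presentation. No rule in either document separates patients who died from survivors in the NYHA shift table, so the table can look more favourable than the true end status. If mortality were 7.3% to 8.9%, up to about 73 to 89 of 1000 patients would be affected. If death is also ranked below class IV, worsening is understated by 0 to 8.9 points.

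A reader might go further and conclude that functional status will look better than it was, by some definite amount such as 4 points. The documents do not support that. The effect is zero where the last class had already worsened, and the 4-point figure needs about half of those who died to carry an unchanged or improved class, for which there is no basis in the text. This study's own mortality is not given either. The table is descriptive, in a single-arm study whose tests are all exploratory, so this is a worthwhile improvement and not a flaw that threatens the study's conclusions.

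**What to change.** In SAP 8.2.4.2, add a separate 'died' column on the final-visit side. Fill it from the survival confirmation in Protocol 7.3.9; SAP 8.2.2 (Follow-up Status) already distinguishes patients who died by Week 52. Footnote how many of these patients had a last recorded NYHA class, and how many had stopped treatment and been assessed before death. If a proportion counting death as worsened is wanted, show it only as a supplementary summary, labelled as such.

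The cost is one extra column and a footnote, with no new data collection. The drawback is that the last class of patients who died after discontinuation moves from the body of the table to the footnote.
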